4.2 Duration/Patient Flow

The length of time to complete research and clinical training, treatment (BSFT, TAU), and data collection (B1-T12) is shown in (see Table 3, section 12.0). Clinical training takes approximately 5 months to complete, whereas protocol-specific research training may be completed in one to two weeks. Research and clinical training may occur simultaneously or may be staggered depending on Node/CTP training resources. Clinical training will occur in the five-month period prior to beginning randomization of participants.

The expected length (months) of the total protocol for a CTP 29 months. This estimated timeframe is based on a rate flow of 60 cases available for randomization of youths per CTP. CTPs with a more substantial case flow may be involved for a shorter period of time, or provide a larger number of youths, if needed. CTPs with a less substantial case flow may take longer to recruit participants. The enrollment period will last approximately twelve months. Therefore, the total duration of the protocol will be approximately 29 month.

Each CTP will provide approximately 60 participants. CTPs with a smaller case flow will be able to participate in the protocol.

4.3 Informed Consent/Human Subjects Safety

Informed consent/assent will be obtained prior to initiating data collection. Prospective participants will receive a copy of the informed consent/assent documents. Consent/assent forms will be read or explained to participants by a research assistant, and participants will also be given ample time to read the informed consent document. Informed consent/assent procedures and forms will be conducted in Spanish or English according to the language prospective participants are most comfortable reading and speaking (a Spanish version will be made available by the Lead Node). Participants will be encouraged to ask questions to clarify any aspect of the study. A brief test (modeled after an instrument utilized in existing research practices, i.e., Joffe, Cook, Cleary, Clark, & Weeks, 2001) will be utilized to assess if eligible participants understand key aspects of the study. An instrument appropriate to each consent/assent form will be developed. Potential participants must correctly understand all questions before they are asked to sign consent/assent forms. Areas assessed include participants' (adolescents and participating family members) understanding that: a) that this is a research study, b) that their participation is voluntary, and c) that they can withdraw at any time. In addition, participants must demonstrate sufficient comprehension of other aspects of the study including its purpose, procedures (including duration, interventions, videotaping, etc.), and risks specific to BSFT. Consent forms will be signed only after it is clear that eligible participants understand all aspects of the study/protocol. Any incorrect responses should be explained and verbally re-asked until the potential participant demonstrates that s/he understands the item.

Any individual that participates in any aspect of the study, including assessments therapy, or videotaping must sign informed consent/assent forms. In BSFT, when individuals are added to the family therapy group, they will be consented prior to participation.

4.4 Eligibility Criteria

Participants will be included if they are ages 12 to 17 inclusive and have used illicit drugs, other than alcohol or tobacco, in the 30-day period preceding the baseline assessment. Adolescents referred from an institution (e.g., detention, residential treatment, court etc.) will be included even if they do not report drug use in the 30-day period preceding the baseline assessment). Adolescents must currently live with or be expected to live with formal or informal “family”. Family is defined as any individual(s) who serve in the legal or traditional role of family members. However, placements in foster care settings will be excluded from the study. After randomization, adolescents must reside in the same geographical area of a CTP, within an “area” designated by each CTP (see section 4.5 below). Adolescents will be excluded if they are expected to be released to a halfway house, institution, independent or assisted living facility, foster care, or to a location outside of the designated geographical area.

4.5 Inclusion Criteria

- 1) Adolescent between the ages of 12-17 (inclusive).
- 2) Adolescent who used any illicit drug (other than alcohol and tobacco) in the 30-day period that preceded the baseline assessment or that is referred from an institution (e.g., detention, residential treatment, court etc.) to the CTP for the treatment of drug use.
- 3) Adolescent who currently lives with or is expected to live with formal or informal “family.” Family member is defined as any individual who serves in the legal or traditional role of family members, except foster family/home.
- 4) Adolescent and family reside in the same geographical area as their CTP (each CTP will be allowed to set its own radius of operation). This criterion is required because BSFT may involve regular home therapy sessions.
- 5) Adolescent and other family members under 18 years of age will sign informed assent; parent figure(s) and/or legal guardian(s) will sign informed consent to participate in study and to allow adolescent to participate. Attempts will be made to obtain consent from both guardians if guardianship is shared. Only the consent of a biological parent or a legal guardian will be accepted for consenting participation of a youth into this study.

4.6 Exclusion Criteria

- 1) Adolescents that are expected to live in a halfway house, institution, independent or assisted living, foster care, or outside of geographical area will be excluded.
- 2) Adolescents with suicidal or homicidal risk at screening or baseline will be included in the study only after crisis stabilization and consultation with crisis stabilization provider.
- 3) Adolescents with current/pending legal charges for severe offences will be included in the study. However, adolescents with current/pending severe criminal offenses (e.g., murder, attempted murder, aggravated assault, sexual battery/assault) that may result in short- or long-term incarceration will be excluded² to maximize their availability to the protocol. Adolescents who are otherwise court involved will be included.
- 4) Adolescents from non-restricted settings will be excluded if they are already receiving regular (approximately 1 or more sessions per week) treatment services for drug abuse.

² This is done to maximize the likelihood that adolescents will remain available for treatment, and that charges that occurred prior to entry into the study do not affect availability for follow-up assessments.

4.7 Subject Discontinuation Criteria

4.7.1 Required Termination

Participants and family members will be terminated from the study when they state they no longer want to participate, hence, at the participant's request all assessments will be stopped. However, participants that are withdrawn from a treatment condition (i.e., stop attending treatment, or ask to discontinue treatment, or break the agency's rules) will continue to be included in the study, and assessments will still be conducted.

4.7.2 Withdrawal of Participants

Adolescent and family members may be withdrawn from the treatment condition in the event the adolescent: a) attempts suicide with the intent to die, b) reports homicidal ideation with the intent to kill, or, c) dies.

It should be noted that removal from the treatment protocol does not mean removal from analysis. This is an "intent to treat" design. Therefore, every participant that is randomized will be analyzed.

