10.1.1 Overview of Analysis

Testing of Distributional Assumptions. Statistical tests for univariate and multivariate normality (tests of skew & kurtosis) as well as visual inspections of the empirical distributions will be conducted. For all hypotheses residuals from the statistical analysis will be examined to determine that distributional assumptions are met. If these analyses show significant deviations non-parametric, or non-normal based versions of the proposed hypothesis tests will be devised. For example, for count data of small range, Poisson regression is indicated (Koch, Atkinson & Stokes, 1986).

Sampling and Generalizability. To establish comparability for subsequent analyses, comparisons of demographic characteristics between the following groups of participants will be conducted: participants who agree to participate (sign consent), and participants who are randomized. Analyses will also document the reasons for non-eligibility and reasons for non-participation of those eligible. Further comparisons will be made to the groups that remain in the study through various assessment times as described below in Missing Data and Attrition.

Urn Randomization. Randomization will be conducted separately by the CTP using a telephone call-in procedure developed by the Veteran's Affairs. This procedure uses an urn randomization program to increase the likelihood that treatment groups are balanced on two characteristics: Ethnicity/ race (Hispanic, African-American, other) and Level of Drug Use (any drug diagnosis other than alcohol or tobacco, no drug diagnosis) at baseline. This will ensure balance across the two treatment conditions.

All variables included as factors in the urn program will be included as covariates in the primary test of the intervention effectiveness. In addition, age, gender, baseline levels of psychiatric co-morbidity status (no comorbidity, externalizing disorder/s, internalizing disorder/s, internalizing and externalizing disorders), primary drug of abuse, family type and family-peer functioning will be controlled due to their anticipated relationship to most of the outcomes.

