Missing Data and Attrition. Analyses will be conducted to identify patterns of attrition and to determine if there is differential attrition by treatment condition. Attrition between conditions will be captured with the use of contact logs, and termination forms. To minimize any impact of attrition on the test of hypotheses, intent-to-treat analyses will be conducted for all hypotheses. Note that individuals that are placed in more restrictive settings for brief periods of time may continue to be included in subsequent assessments. Data will be collected for these individuals at all scheduled timepoints (if possible). The primary outcome measure will be used to identify days that the adolescent was placed in a restrictive environment.

Missing items from multi-item scales will be imputed using the Expectations Maximization (EM) algorithm (Little & Rubin, 1987); however, missing outcome measures (e.g. caused by missing an assessment) will not be imputed. Rather, the hypotheses will be modeled in an intent-to-treat fashion with a maximum likelihood algorithm, which allows the inclusion of cases with missing data (this is possible with the assumption that data are missing

at random). Note that the protocol calls for continued assessment of cases that drop out of intervention in the hope of minimizing all forms of missing data.

Reliability. When appropriate, reliability of all measures and outcomes will be assessed using confirmatory factor analysis. To confirm internal consistency reliability, estimates of Cronbach's alpha for each of the outcome variables (e.g., drug use, externalizing problem behaviors, family functioning) will be determined with a confirmatory factor analysis (Fornell & Larcker, 1981). The indicators of the outcomes in this protocol are scales of established reliability and validity. For any indicator/scale with an alpha < .70 (in this sample), items with low item-total correlations will be trimmed from the scale and the scale re-assessed for reliability. In the confirmatory factor analyses of the outcome variables based on these indicator/scales, should the overall fit of these models prove inadequate (Comparative Fit Index < .95 or standardized root mean squared residual > .06 (Hu & Bentler, 1999; Kline, 1998), additional modifications of the measurement model will be made to achieve an adequate fit. Specifics of the measurement models are described below under "Outcomes and Hypotheses".

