10.2 Primary Outcome and Hypothesis

Hypothesis 1. BSFT will be significantly more effective than TAU in reducing adolescent drug abuse, defined as the percentage of drug use days in 28-day periods.

Outcome Variable. The outcome variable for this hypothesis is the percentage of days of drug use within a 28-day period. This variable will be constructed from the Timeline-Follow-back instrument and will be measured as the sum of the number of days with positive use in 28-day increments (there are thirteen 28-day periods in this design, B1 and T1-T12). Periods in which the participant is in a restricted environment will be flagged in the database, but will be included in the primary analysis. If there is missing information on the time-line follow-back within a 28-day period, the percentage will be calculated as the percentage of available days in that period, as long as not more than 14 days are missing. There is a chance that data collected at the same assessment point are more related than data collected across assessment points. Our data analysis strategy exploits the nested structure of our data. Thus, in this protocol, 28-day measures of drug use are nested within 13 assessment points, these assessment points are nested within individuals, individuals are nested within community treatment providers. The statistical model, as defined below, accommodates these different nesting factors. From our experience, in models with many levels of nesting, it is not uncommon for some of the random effects associated with these levels to have close to zero variance. Thus, our strategy will be to first examine the trajectories (blind to the condition assignment), and to

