HLM conceptualizes the growth curve as separate equations for the intercept and another equation or other equations (if more than linear change is examined) for the slope, though both (all) are estimated jointly. With the addition of treatment site as a random effect, this model is a three level HLM model. These three levels are associated with 1) time, 2) individual and 3) site. There is an additional level, or random effect associated with the nesting of 28-day periods within an assessment. As noted above, prior to testing hypotheses, in an analysis blind to condition, we will fit these 4 different levels (and additional polynomial terms). If any of the random components, or polynomial terms are not significantly different from zero, we will drop them from the model. Note that in the presentation that follows, we just present the substantive levels of the individual and omit the higher order polynomial terms to focus the exposition on the substantive issues (the growth curve and site variation). To facilitate interpretation of the growth curve, time will be centered on the 4-month post-randomization assessment (T4). Thus, the intercept term represents the difference between the two conditions immediately post intervention. If the expected ordinal nature of the outcome measure results in sufficient deviation from normality a Poisson link function will be used.

10.2.1 Level 1

For Hypothesis 1, the time path of percentage of days having used drugs in 28-day periods will be estimated and the growth trajectory will be parameterized to be a function of BSFT intervention status. Additional predictors will be the stratification variables specified in the urn randomization and the other variables, described under the heading randomization (see section 10.1.1) and any baseline variables found to predict the occurrence of missing data. The growth curve analysis will include the times after baseline only, and baseline value of the dependent measure will be included as a covariate (i.e. an analysis of covariance parameterization). The presentation below does not include the baseline value of drug use or

these other additional covariates, to ease the exposition. As mentioned this is a three-level HLM model. Level 1 describes the trajectory over time for an individual participant:

Level 1

$$y_{ijt} = \pi_{ij0} + \pi_{ij1} \cdot a_{ijt} + \varepsilon_{ijt},$$

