$$y_{ijt} = [(\gamma_{000} + u_{0j0}) + (\gamma_{100} + u_{1j0})BSFT + r_{ij0}] + [(\gamma_{001} + u_{0j1}) + (\gamma_{101} + u_{1j1})BSFT + r_{ij1}] \cdot a_{ijt} + \varepsilon_{ijt}$$

or,

$$y_{ijt} = [(\gamma_{000} + \gamma_{100}BSFT) + (\gamma_{001}a_{ijt} + \gamma_{101}BSFT * a_{ijt}) + (\varepsilon_{ijt} + u_{0j0} + u_{1j0} * BSFT + u_{0j1} * a_{ijt} + u_{1j1} * BSFT * a_{ijt} + r_{ij0} + r_{ij1} * a_{ijt})]$$

This model will be estimated using either SAS Proc Mixed (or Proc NLMixed if a non-linear link function is necessary).

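### The promise that every randomized youth will be analyzed does not fit the Hypothesis 1 model, which has no place for a youth without a valid follow-up period and no stated rule for a wholly missing baseline covariate

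*Protocol*

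**What the plan says.** Section 4.7.2 deals with youths withdrawn from a treatment condition. It states that "removal from the treatment protocol does not mean removal from analysis", calls the design intent-to-treat, and concludes: "Therefore, every participant that is randomized will be analyzed". Section 10.1.1 (Missing Data and Attrition) repeats intent-to-treat for all hypotheses. It says maximum likelihood, under a missing-at-random assumption, lets cases with missing data be included.

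The rules that decide who enters the Hypothesis 1 model are these:

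- **Responses (10.2.1):** "The growth curve analysis will include the times after baseline only, and baseline value of the dependent measure will be included as a covariate".
- **Missing outcomes (10.1.1):** "missing outcome measures (e.g. caused by missing an assessment) will not be imputed".
- **Valid period (10.2, Outcome Variable):** a percentage is computed from the available days "as long as not more than 14 days are missing".
- **End of assessment (4.7.1):** "at the participant's request all assessments will be stopped".
- **Covariates (10.1.1):** the two urn factors, plus age, gender and comorbidity, and "primary drug of abuse, family type and family-peer functioning will be controlled". Section 10.2 adds institutional referral. Section 10.2.1 adds baseline drug use and any baseline variable found to predict missingness.
- **Imputation (10.1.1):** EM, for missing items within multi-item scales only.
- **Software (10.2.3):** "This model will be estimated using either SAS Proc Mixed", or NLMixed if a non-linear link is needed.

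**The concern.** The sentence in 4.7.2 covers everyone randomized, and its list of reasons for withdrawal includes death. It therefore reaches youths who may have no follow-up at all. The model has no row for them. If baseline drug use were part of the response vector, a youth with baseline data only would still enter the likelihood. Section 10.2.1 makes it a covariate instead.

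The covariate list opens a second gap. A likelihood fit copes with missing responses, but a record with a missing predictor is dropped by default in the software named. The EM step does not reach a form that was never completed, or single items such as family type or primary drug. Some inputs need a parent: two of the four parenting scales come from parents only (7.7.7), and the DISC Predictive Scales use parent as well as adolescent report. B1 is one of the thirteen 28-day periods in 10.2, so the 14-day rule could also void baseline use.

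At stake is what the primary result may be called. A report that all 480 youths were analyzed would be inaccurate, and one missing-at-random fit cannot show what the absent youths would have done to the estimate.

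**Working it through.** **1. Who is in the model.** Put the rules together for a youth who withdraws from assessments soon after randomization, or whose every follow-up period has more than 14 missing days. Baseline is not a response, no T1–T12 period has a value, and nothing is imputed. The youth supplies no response, so the primary estimate does not use that youth. This follows from the protocol text alone.

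**2. The plan's own power figures.** Section 10.4.1 gives 87%, 75% and 64% for small, moderate and high site variability, with J = 8 sites, effective n = 57 per site and δ = .45. The values .10 and .15 for σδ² are printed. The value for small variability is lost from the text, and .05 is assumed. A two-sided alpha of .05 is also assumed.

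- Formula: λ = Jδ² / (σδ² + 4/n), referred to a noncentral F with 1 and J − 1 = 7 degrees of freedom.
- Jδ² = 8 × .2025 = 1.62 and 4/57 = .0702.
- λ = 1.62/.1202 = 13.5, 1.62/.1702 = 9.5 and 1.62/.2202 = 7.4.
- Power = .881, .754 and .645. The stated figures reproduce to within about one point.

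**3. Youths with no follow-up.** The only attrition figure is 28% over 12 months (10.4.1). How it falls over time is an assumption.

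- Even spread over 12 periods: .28/12 = 2.3%, and 480 × .0233 = 11.2 youths lost before the first period.
- Constant hazard: 1 − .72^(1/12) = 2.7%, and 480 × .027 = 13.0 youths.

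**4. Youths with a wholly missing covariate.** Baseline precedes randomization. The urn factors are needed to randomize, and age, referral and recent drug use belong to eligibility. About five covariates can then plausibly be missing: comorbidity, primary drug, family type, family functioning and peer functioning. With each missing independently in a proportion m (assumed), the share with at least one missing is 1 − (1 − m)^5:

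| m | share | of 480 |
|---|---|---|
| 0.5% | 2.5% | 12 |
| 1% | 4.9% | 24 |
| 2% | 9.6% | 46 |

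If one uncompleted form causes several gaps in the same youth, the total is smaller, so these counts are near the upper end for each m.

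**5. Power cost.** Replace n = 57 by 57 × (1 − loss):

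| loss | analyzed | small | moderate | high |
|---|---|---|---|---|
| 0 | 480 | .881 | .754 | .645 |
| 5% | 456 | .871 | .745 | .638 |
| 10% | 432 | .861 | .735 | .630 |
| 15% | 408 | .849 | .725 | .622 |

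Steps 3 and 4 sum to between 11 + 12 = 23 youths (4.8%) and 13 + 46 = 59 youths (12.3%). A loss of 5% to 10% costs about 1 to 2 points. The top of the summed range stays below the 3.2 points lost at 15%.

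**6. Bias, as an illustration.** Suppose all 13 youths without follow-up were in one arm of 240 and were 0.5 SD worse than the model predicts (both assumed). The contrast would move by (13/240) × 0.5 = .027 SD, against a design effect of .45. Covariate gaps arise before randomization, so between the arms they can differ only by chance.

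**The case against.** The strongest reply is that 4.7.2 is about treatment withdrawal and that its purpose is met. Sections 4.7.1 and 4.7.3 keep youths who leave treatment in assessment, and they are analyzed in their assigned arm. A reader might infer that no intent-to-treat analysis is delivered at all, but the protocol does not support that. What stands against the reply is only the literal claim about everyone randomized.

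Next, no section says that a youth with a missing covariate is dropped. That is inferred from software behaviour, and a rule could sit in an analysis plan that is not shown. This is fair, and it makes the covariate part a risk rather than a contradiction. The statement in 10.1.1 that likelihood estimation lets cases with missing data be included is still broader than the method.

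A reader might also take the engagement rates in 1.3.2 (81% against 60%, and 92.9% against 42.3%) as a forecast of unequal loss by arm. They are not one. They count families completing intake, or intake plus a first session, in earlier studies, and in the second pair both arms received BSFT. Here follow-up does not depend on attending therapy. A separate blinded assistant collects drug use (5.4.2), with reminders, contact persons and incentives (7.5, 7.9). The TLFB at each visit reaches back to the previous one (7.7.2), so a missed T1 can be recovered at T2.

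Finally, 10.1.1 already plans a comparison of attrition by condition, and 10.2.1 adds predictors of missingness as covariates. Both help, but neither brings in a youth with no response.

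**Conclusion.** The point holds, and it is minor. On the protocol's own text, a youth with no valid T1–T12 period is not in the Hypothesis 1 analysis, so the statement in 4.7.2 is not literally true. The handling of a wholly missing baseline covariate is not stated, and under the software default it would remove youths whose outcomes were collected.

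The likely size is about 11 to 13 of 480 youths without follow-up, resting on the 28% attrition and an assumed time pattern. At most about 12 to 46 would lack a covariate, resting on five covariates and assumed rates of 0.5% to 2%. Power is hardly affected. If outcomes are missing at random given the covariates, leaving out youths with no follow-up does not bias the contrast. If they are not, a modest bias is possible, and the planned single analysis would not reveal it. The documents do not support a forecast of large loss or of strongly unequal loss by arm.

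**What to change.** 1. In 4.7.2 and 10.1.1, state the set actually analyzed for Hypothesis 1: youths in their assigned arm with at least one valid post-randomization period. Keep the statement that leaving treatment does not remove a youth from analysis. Report by arm how many randomized youths have no valid period.
2. In 10.1.1, fill wholly missing baseline covariates by single imputation blind to arm, either by extending the EM step already used for scale items or by mean or mode. No youth with outcome data is then dropped.
3. Add one sensitivity analysis of Hypothesis 1 on all randomized youths, with delta-adjusted (pattern-mixture) imputation for those with no valid period and the range of delta fixed in advance.

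The cost is a few lines of text, one imputation step and one extra sensitivity run. No new data are needed.
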